Study Protocol

Randomized Evaluation of Heart Failure with Preserved Ejection Fraction (HFpEF) Patients with Acute Heart Failure and Dopamine (ROPA-OP) Trial

clinicaltrials.gov Identifier: NCT01901809

Protocol Date: August 8, 2013

Principal Investigator:

[name]

The Johns Hopkins University School of Medicine.

[name]

[name]

[contact] [contact]

JHM IRB - eForm A – Study Protocol

- Use the section headings to write the JHM IRB eForm A, inserting the appropriate material in each. If a section is not applicable, leave heading in and insert N/A.
- When submitting JHM IRB eForm A (new or revised), enter the date submitted to the field at the top of JHM IRB eForm A.

1. Abstract

- a. Provide no more than a one page research abstract briefly stating the problem, the research hypothesis, and the importance of the research.

Heart Failure with preserved Ejection Fraction (HFPEF) accounts for 40-50% of all heart failure patients with a frequency of hospital admissions for acute decompensation and short and long term mortality similar to patients with heart failure with reduced ejection fraction (HFREF). Patients with HFPEF are often preload dependent and despite admission to the hospital for acute decompensated heart failure (ADHF), are typically difficult to diurese due to the development of acute kidney injury. In contrast to the many randomized trials showing mortality and morbidity benefit of ACE inhibitors and beta blockers in patients with heart failure with reduced ejection fraction, no drugs have shown a benefit in patients with HFPEF. Furthermore, patients hospitalized for ADHF who develop acute kidney injury during their hospital stay have longer hospitalizations, more frequent re-hospitalizations for heart failure, and worse short term survival compared to those without acute kidney injury. We hypothesize that changing the method of diuresis and/or the addition of low-dose dopamine for the treatment of ADHF in patients with HFPEF will reduce renal injury, resulting in a shorter length of stay, and decrease hospital readmissions over the ensuing year.

2. Objectives (include all primary and secondary objectives)

To evaluate the effects of low dose dopamine and diuretic strategy (intermittent versus continuous) on renal function in patients with HFPEF admitted with acute heart failure.

Primary end point:

1. Percent change in creatinine from randomization to 72 hrs from treatment protocol initiation.

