6. Drugs/ Substances/ Devices

a. The rationale for choosing the drug and dose or for choosing the device to be used.

Furosemide is that standard of care diuretic for patients admitted to the hospital for acute decompensated heart failure. Dopamine at low dose is often used to assist diuresis and reduce acute kidney injury in patients at high risk for acute kidney injury with heart failure from systolic dysfunction.

b. Justification and safety information if FDA approved drugs will be administered for non-FDA approved indications or if doses or routes of administration or participant populations are changed.

N/A.

c. Justification and safety information if non-FDA approved drugs without an IND will be administered.

N/A

7. Study Statistics

a. Primary outcome variables.

1. Percent change in creatinine from randomization to 72 hrs from treatment protocol initiation.

b. Secondary outcome variables.

1. Change in incidence of acute kidney injury (AKI) as defined by Kidney Disease: Improving Global Outcomes (KDIGO criteria summarized below) from randomization to 72 hrs.¹
2. Incidence of AKI as determined by urine output at 72 hrs (KDIGO criteria, summarized below).¹
3. Change in creatinine at 72 hrs adjusted for volume of fluid removal
4. Change in serum cystatin C randomization to 72 hrs
5. Change in NT pro-BNP from randomization to 72 hrs
6. Volume of diuresis measured in liters
 - c) Cumulative volume of diuresis measured in liters
 - d) Cumulative volume of diuresis measured in liters adjusted for BSA
7. Net weight loss at 72 hrs in kg
8. Need for increase in intravenous diuretic dose
9. Change in distance during 6 minute walk test
 - c) From admission to 72 hrs
 - d) From admission to discharge
10. Global well-being assessment score from admission to 72 hrs, and at discharge. To be assessed by a Visual Analog Scale (VAS).
11. Subjective dyspnea score from admission to 72 hrs, and at discharge. To be assessed by a Visual Analog Scale (VAS).
12. Change in frailty index from admission to 72 hrs, and at discharge. To be assessed by the Johns Hopkins Older Americans Independence Center Online Frailty Assessment Tool
13. Length of stay of hospitalization in days

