14. 30 day, 6 month, and 1 year hospital readmission or ER visit for major adverse cardiovascular event, heart failure, renal failure (development of CKD, ESRD, or dialysis need by KDIGO criteria), syncope, or arrhythmia. Readmission events will be adjudicated by a Clinical Event Committee consisting of 2-3 cardiologists not directly in contact with patients enrolled in the study.

KDIGO AKI Definition¹:

AKI is defined by any of the following 3 criteria:

1. Increase in serum creatinine by ≥ 0.3 mg/dl (≥ 26.5 $\mu\text{mol/l}$) within 48 hours; OR
2. Increase in serum creatinine to ≥ 1.5 times baseline, which is known or presumed to have occurred within prior 7 days; OR
3. Urine volume < 0.5 ml/kg/h for 6 hours

Stages of AKI as defined by KDIGO Criteria are as follows:

Stage	Serum Creatinine	Urine Output
1	1.5-1.9 times baseline OR ≥ 0.3 mg/dl (≥ 26.5 $\mu\text{mol/l}$) increase	< 0.5 ml/kg/h for 6-12 hours
2	2.0-2.9 times baseline	< 0.5 ml/kg/h for ≥ 12 hours
3	3.0 times baseline OR increase in serum creatinine to ≥ 4.0 mg/dl (≥ 353.6 $\mu\text{mol/l}$) OR initiation of renal replacement therapy OR, in patients < 18 years, decrease in eGFR to < 35 ml/min per 1.73 m ²	< 0.3 ml/kg/h for ≥ 24 hours OR Anuria for ≥ 12 hours

a. Statistical plan including sample size justification and interim data analysis.

1. Overview:

- a. This is a factorial design study evaluating two simultaneous unrelated interventions. Sample size justification and primary endpoint analysis is described below.

2. Analysis of Primary Endpoints:

- a. The primary analysis will be conducted on an intention-to-treat basis. Non-parametric testing for the continuous primary endpoint (creatinine) will be performed using the Wilcoxon-Mann-Whitney U test. Confirmatory test for interaction between dopamine and diuretic strategy will be performed with linear regression analysis with dopamine*diuretic term, $p=0.10$ for significance.

3. Sample Size Justification:

- a. A difference of 30% in creatinine pre and post- treatment is considered to be clinically meaningful. Setting parameters as follows: two-sided, alpha (Type I error rate) of 0.05, power of 0.80, and using mean creatinine calculations based on our own retrospective experience at

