Johns Hopkins as well as data from prior studies in patients admitted with ADHF, we estimate a sample size of approximately 63 patients per treatment arm. This translates to 63 patients assigned to the diuretic-only treatment arm (intermittent bolus and continuous) and 63 patients assigned to the low-dose dopamine arm (in addition intermittent bolus diuretic and continuous diuretic treatment). Taking into account drop-out rate, we plan to enroll 140 patients (70 per treatment arm; 34 per specific treatment strategy).

4. Randomization:

- a. Patients will be randomized in a blinded fashion to one of four treatment arms upon enrollment. We plan to perform block randomization into the treatment arms and plan to stratify patients by race, CKD status, and receipt of IV contrast dye (during the same admission), as these factors are felt to be significantly associated with the development of AKI.

5. Analysis of Secondary Endpoints:

- a. Summaries of continuous variables will be displayed using the mean, standard deviation, and median. For nominal variables, the number and frequency of subjects in each category will be presented. Statistical tests with p-values < 0.05 will be considered statistically significant, unless otherwise stated.

b. Early stopping rules.

A study subject will be removed from the trial if the above mentioned scenarios from Section 5 were to occur:

- i. The development of hemodynamic instability including hypotension (SBP < 90), hypertensive emergency, or unstable arrhythmias (SVT or VT)
- ii. The development of pulmonary edema requiring inotropes or vasopressor or more than 50% inspired oxygen.
- iii. The development of acute coronary syndrome.
- iv. The development of acute kidney injury as follows:
 - a. If the patient develops Stage II AKI (by KDIGO criteria)¹, the study treatment will be held and a clinical decision will be made whether to resume or discontinue treatment drug
 - b. If the patient develops Stage III AKI (by KDIGO criteria)¹, the study treatment will be discontinued and the patient will be classified as treatment failure and followed only for outcome recording.
 - i. The need for renal replacement therapy
 - ii. New atrial fibrillation or other supraventricular tachyarrhythmia
 - iii. Sustained ventricular arrhythmias

- v. Requirement of furosemide dose increase beyond the study maximum of 200 IV twice daily (or 400 IV over 24 hrs), or the need for addition of thiazide diuretic.

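### Every secondary result with p below 0.05 is to be called significant without hierarchy or exploratory label, and the primary analysis does not name which factor contrast or contrasts it tests

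*Combined protocol and SAP*

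**What the plan says.** **Hypothesis and objective.** The abstract hypothesizes that "changing the method of diuresis and/or the addition of low-dose dopamine for the treatment of ADHF in patients with HFPEF will reduce renal injury", and goes on to shorter stay and fewer readmissions. Section 2 gives the objective as "To evaluate the effects of low dose dopamine and diuretic strategy (intermittent versus continuous) on renal function". It names both factors and ranks neither.

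**Primary endpoint and test.** There is one primary endpoint: "Percent change in creatinine from randomization to 72 hrs from treatment protocol initiation". The statistical plan in Section 7 opens with "This is a factorial design study evaluating two simultaneous unrelated interventions". Item 2 (Analysis of Primary Endpoints) specifies intention to treat and a Wilcoxon-Mann-Whitney test but does not say which groups are compared. It adds a regression test for interaction, judged at 0.10.

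**Sizing.** Item 3 gives the only error rate for the primary comparison: "Setting parameters as follows: two-sided, alpha (Type I error rate) of 0.05, power of 0.80". It then describes a single contrast, with "63 patients assigned to the diuretic-only treatment arm" and another 63 on dopamine, each pooled over furosemide strategy. No calculation is given for continuous versus bolus furosemide.

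**Secondary endpoints.** Sections 2 and 7 list 14 numbered items, several with sub-items or more than one time point. Item 5 of the statistical plan describes summary statistics and then sets one rule: "Statistical tests with p-values < 0.05 will be considered statistically significant, unless otherwise stated".

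**The concern.** There are two gaps, and they concern different families of tests.

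The first is the secondary rule. Followed as written, it attaches the word significant to any secondary comparison below 0.05, however many are run. With a list this long, a trial in which neither intervention works would still be expected to yield one or two such findings. Some of the outcomes, notably length of stay and readmission, are ones that readers may act on.

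The second is the primary contrast. The objective covers two factors, the sizing covers one, and the test sentence names none. The hypothesis joins the factors with and/or, so a positive result on either could be presented as confirming it. Treatment is open, and nothing written in advance fixes whether the confirmatory result is the dopamine contrast, the diuretic contrast, or whichever is positive.

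**Working it through.** **1. The plan's own figure.** No standard deviation is given, so 63 per arm cannot be rebuilt from the stated inputs alone. Assume a standardized effect d = 0.50, which for a 30-point difference means an SD of 60 points. Then n = 2(1.960 + 0.842)² / 0.50² = 62.8, rounded up to 63, with power 80.1%. In steps of 0.001, only d from 0.500 to 0.503 gives 63; d = 0.45 gives 78 and d = 0.55 gives 52. So the stated size is consistent with one two-group comparison at an undivided 0.05. It contains no allowance for a second contrast under that assumption.

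**2. Number of secondary results** (list in Sections 2 and 7)

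| Items | Results |
|---|---|
| 1 to 5 | 5 |
| 6 (two versions) | 2 |
| 7 and 8 | 2 |
| 9 (two intervals) | 2 |
| 10, 11, 12 (72 hours and discharge) | 6 |
| 13 | 1 |
| 14 (30 days, 6 months, 1 year) | 3 |
| Total | 21 |

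With two factors, counting each numbered item once gives 14 × 2 = 28 tests. Counting every outcome and time gives 21 × 2 = 42.

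**3. Expected false positives if neither factor affects anything.** 28 × 0.05 = 1.4 and 42 × 0.05 = 2.1. Correlation between outcomes does not change these expectations.

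**4. Chance of at least one.** Under independence, 28 tests give 1 − 0.95²⁸ = 76.2% and 42 tests give 1 − 0.95⁴² = 88.4%. The outcomes overlap, so independence is an upper case. Simulation used 21 equally correlated results per factor, with the two factors independent of each other:

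| Common correlation | Chance of at least one in 42 |
|---|---|
| 0 | 88% |
| 0.3 | 80% |
| 0.5 | 68% |
| 0.8 | 40% |

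The correlations are assumptions; the documents give none.

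**5. Primary endpoint, if both pooled contrasts are tested at two-sided 0.05.** Allocation is 1:1:1:1 (Section 4.a), so the two contrasts are nearly independent. The chance of at least one false positive in either direction is 1 − 0.95² = 9.75%. A null simulation of the 2×2 design with 35 per cell and two Wilcoxon tests gave 9.5%. If only a beneficial result counts as support, each test contributes 0.025, and the chance is 1 − 0.975² = 4.9%, against 2.5% for a single contrast. The interaction test is a check on the factorial assumption and is not counted.

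**The case against.** The strongest reply is that a factorial trial of distinct interventions may spend 5% on each question. The plan calls its interventions unrelated, and 0.05 appears as the alpha of a sizing calculation, not as a promise about the whole study. This stands. A reader might infer that the trial has double its promised error rate. The documents do not support that, because no study-wide rate is promised and testing both factors is itself an inference from the objective and the design.

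It is also fair that the hypothesis is directional, so 9.75% includes results showing harm; for benefit alone the figure is 4.9%. The and/or sentence comes from an abstract and continues to other outcomes. Section 7 states no rule that either factor makes the trial positive.

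On the secondary side, 42 is an upper count. Item 5 gives summaries and a general threshold and does not list tests by factor. A reader might conclude that a spurious secondary finding is nearly certain, but that holds only close to independence. Nor does the plan describe pairwise tests among the four arms, so no error rate should be computed for them.

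Two things survive. The secondary threshold is a written rule with no exploratory label. And the convention of 5% per question is nowhere stated, while the hypothesis is worded jointly.

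**Conclusion.** The point holds in two separate parts, whose error rates should not be combined into one figure.

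*Secondary endpoints.* The rule would be expected to label between one and two null results significant (1.4 to 2.1), assuming that each outcome is tested for both factors. The chance of at least one among 42 runs from about 40% to 88%, depending on correlation. This is the firmer part, because it follows from a rule that the plan states.

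*Primary endpoint.* The defect is an unnamed contrast and an unstated error convention, not a demonstrated excess of false positives. The 9.75% (or 4.9% against 2.5% for benefit only) applies on two conditions: both pooled contrasts are tested at two-sided 0.05, and either is taken to support the joint hypothesis. If the two factors are declared separate questions, each keeps its own 5% and there is no inflation to correct.

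**What to change.** **Item 5 (secondary endpoints).** Replace the p-value threshold with between-group estimates and 95% confidence intervals, labelled exploratory and reported without significance claims. The cost is wording. The downside is that all secondary results, including length of stay and readmission, become descriptive.

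**Item 2 (primary endpoint).** Name the pooled contrasts: dopamine versus no dopamine across furosemide strategies, identified as the sized one, and continuous versus bolus across dopamine groups. Then state one of these:

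- The factors are separate questions, each at two-sided 0.05, and the and/or hypothesis is split in two to match. This costs no power, but a joint claim from either result is given up.
- The contrasts are tested in fixed order, dopamine first, with the diuretic contrast confirmatory only if the first is significant. Dopamine keeps its full 0.05. The price is that a confirmatory diuretic claim depends on the dopamine result, although the objective ranks neither factor.

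Dividing alpha is possible but dearer. By the normal approximation with 63 per level and 0.025 per test, power falls from 80.1% to 71.4%. This assumes a standardized effect of 0.50, because no SD is given. At 0.45 it falls from 71.4% to 61.2%, and at 0.55 from 87.0% to 80.1%. Either of the two listed options leaves enrolment and trial procedures unchanged.

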 - a. Intermittent furosemide diuretic therapy from above (1.) with the addition of dopamine at 3 µg/kg/min
4. Continuous infusion furosemide diuretic therapy plus infusion of low dose intravenous dopamine (3 µg/kg/min)
 - a. Continuous furosemide diuretic therapy from above (2.) with the addition of dopamine at 3 µg/kg/min

Conversion guidelines:

2 mg oral furosemide = 1 mg intravenous furosemide

1 mg torsemide = 2 mg furosemide

1 mg bumetanide = 40 mg furosemide

Diuretic titration guidelines:

Should the patient fail to demonstrate adequate diuresis (net negative urine output of at least 500ml in 12 hrs) in response to the first treatment dose, the subsequent diuretic dose to be administered 12 hrs later (dose #2) will be doubled, or the continuous infusion will be doubled, with the goal of net negative urine output of 1 liter over 24 hrs. This titration plan can continue until adequate diuresis is achieved (at least net negative 1L urine output over 24 hr period).

Maximum Diuretic Dose:

The maximum dose permitted within study protocol will be furosemide 200 IV twice daily, or a total dose of furosemide 400 IV over 24 hrs. Should the primary team feel the patient needs higher dosing or the addition of a thiazide diuretic (or alternative agent), the patient will be considered treatment failure and will be removed from the study.

Electrolyte Repletion Guidelines:

The primary team will obtain basic metabolic panels on all study participants every 12 hours for the duration of the study. It will be the responsibility of the primary team to replete electrolytes with the goals of potassium > 4.0, and magnesium >2.0 as needed for study participants.

Fluid and Salt Restrictions:

Each study participant will be maintained on a daily 2 liter fluid and 2 gm sodium restricted diet, to be ordered by the primary team.

Treatment beyond trial end-point guidelines:

Intravenous diuretic therapy with or without dopamine according to the protocol will be continued until the treating physician decides the patient no longer requires intravenous diuretic therapy or 72 hours, whichever comes first.

All other heart failure or non-heart failure treatments will be left to the discretion of the primary team from the time of the patient's admission to the hospital and/or enrollment in the study. This includes anti-hypertensives, anti-arrhythmic drugs, and any other therapies deemed necessary for the treatment of the study subject.

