After 72 hrs, the study drug will be discontinued, a primary assessment will be made of primary and secondary endpoints, and all further treatment is at the treating physician's discretion.

Note: Study participants will be permitted to cross over into non-assigned arms of the study, however the study analysis will be completed as an intention-to-treat study. It will be left to the discretion of the primary team, with supervision from the study investigators as to whether a cross over is necessary within the 72 hr study time frame.

Baseline Assessments and Data to be Recorded (all are standard of care unless indicated by *)

1. Directed history and physical exam, focused on signs and symptoms of congestion/volume overload
2. Vital signs (HR, BP, O2 saturation, weight, height)
3. Home medications
4. Basic metabolic panel including serum creatinine, BUN, electrolytes and magnesium
5. Serum Pro-BNP level
6. Serum Cystatin C*
7. High-sensitivity troponin
8. Baseline electrocardiogram
9. Transthoracic echocardiogram if one has not been obtained within 1 year prior to admission
 - i. Including left ventricular (LV) ejection fraction, LV dimensions, left atrium size (LA), LV mass, right ventricular function parameters (RVSP), valvular assessment
10. 6 min walk test*
11. Patient Global Well being assessment by VAS*
12. Dyspnea assessment by VAS*
13. Frailty Index*
14. Blood sample for biomarkers and genetic testing for heart failure*
15. Urine sample for biomarkers*

24 hr Assessment:

1. Routine vitals assessment with weight recording
2. I/O assessment – to be recorded and totaled for each 12 period
3. Twice daily basic metabolic panel and serum magnesium

72 hr Assessment and Data to be Recorded:

1. Routine vitals assessment with weight recording
2. I/O assessment – to be recorded and totaled for each 24 period
3. Twice daily basic metabolic panel and serum magnesium
4. Serum Pro-BNP level*
5. Serum Cystatin C*
6. High-sensitivity troponin
7. 6 min walk test*
8. Patient Global Well being assessment by VAS*
9. Dyspnea assessment by VAS*
10. Frailty Index*
11. Changes in cardiovascular medications
12. Assessment for serious cardiovascular events

At Discharge Assessment and Data to be recorded:

1. Routine vitals assessment with discharge weight recording
2. I/O assessment – to be recorded and totaled for each 24 period
3. Basic metabolic panel including creatinine, BUN
4. Serum Pro-BNP level
5. Serum Cystatin C*
6. High-sensitivity troponin
7. 6 min walk test*

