8. Patient Global Well being assessment by VAS*
9. Dyspnea assessment by VAS*
10. Frailty Index*
11. Changes in cardiovascular medications
12. Assessment for serious cardiovascular events
13. Urine and serum samples for biomarkers*

*Investigational data to be collected as part of trial protocol.

Day 30, 6 month, and 1 year Assessment and Data to be Recorded:

Patient charts will be reviewed and patients will receive a phone call to assess for potential re-hospitalizations and major adverse cardiovascular events at each respective endpoint since discharge. The first readmission event following index hospitalization will be adjudicated by a Clinical Event Committee consisting of 2-3 cardiologists not directly in contact with patients enrolled in the study.

Vascular Access:

All patients in the intermittent bolus diuretic strategy arm will require the placement of two functioning peripheral IV catheter. Patients assigned to the continuous diuretic strategy and either treatment arm that requires low-dose dopamine will need at least 2 peripheral IVs suitable for continuous infusions. Central venous catheter placement may be required should it be difficult to obtain or maintain peripheral IV

access. This would be determined by the primary team, with consent obtained separately for this procedure by the primary team.

Foley Catheter Placement:

All patients enrolled in this trial will be encouraged to have a foley urinary catheter placed. This will allow for improved patient tolerance of diuresis and improved accuracy of I/O assessment by nursing staff. This will not be required, however, for enrollment in the trial.

b. Study duration and number of study visits required of research participants.

The study duration is the hospital admission. The study drugs will be mandated for 72 hours following enrollment. There are no outpatient visits but patients will receive follow up phone calls, at 30 days and at 6 months following discharge.

c. Blinding, including justification for blinding or not blinding the trial, if applicable.

The treatment is not blinded. The primary endpoint of change in renal function will be objectively obtained and should not be affected by lack of blinding. All other variables will be obtained by an investigator blinded to the study drug assignment.

d. Justification of why participants will not receive routine care or will have current therapy stopped.

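### The intention-to-treat primary test needs a 72-hour creatinine, but the plan gives no way to include patients discharged or removed before 72 hours

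*Combined protocol and SAP*

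**What the plan says.** Sections 2 and 7 define the primary endpoint as "Percent change in creatinine from randomization to 72 hrs from treatment protocol initiation". In section 7, Analysis of Primary Endpoints states: "The primary analysis will be conducted on an intention-to-treat basis". The test is Wilcoxon-Mann-Whitney, with a linear regression for the dopamine-by-diuretic interaction. No rule is given for a missing 72-hour value.

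On treatment duration, section 4.a (Treatment beyond trial end-point guidelines) continues therapy "until the treating physician decides the patient no longer requires intravenous diuretic therapy or 72 hours, whichever comes first". Section 4.b says: "The study drugs will be mandated for 72 hours following enrollment".

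On sampling, section 4.a (Electrolyte Repletion Guidelines) asks for metabolic panels every 12 hours while the study lasts. The 24-hour and 72-hour lists repeat this ("Twice daily basic metabolic panel and serum magnesium"), and creatinine is also drawn at discharge. Section 4.b adds "The study duration is the hospital admission", with telephone follow-up and no outpatient visits.

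On treatment failure, section 4.a (Maximum Diuretic Dose) takes patients who need more than the permitted dose or an added agent out of the study. Section 4.f speaks of removal from the protocol and keeps Stage III AKI cases for outcome recording. Section 7.b speaks of removal from the trial.

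On loss, the Sample Size Justification says only: "Taking into account drop-out rate, we plan to enroll 140 patients". No drop-out rate is stated.

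**The concern.** A rank test on one landmark needs that landmark for every patient analysed. Here the value can be absent for reasons tied to the patient's course. One who decongests quickly may go home before 72 hours, and one who fails treatment may be removed. Section 1 hypothesises less renal injury and a shorter stay, so if the hypothesis is right, early discharge could differ by arm.

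Section 4.c argues that an objective creatinine is not affected by open-label treatment. That covers how the value is measured. It does not cover whether a 72-hour value exists, because stopping, discharge and removal are decided by clinicians who know the assignment.

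Extra enrolment restores the number of patients but does not restore the randomised comparison. Meanwhile the 12-hourly creatinine values, already collected, have no role in the primary analysis.

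**Working it through.** **1. The plan's own figures.** Inputs from section 7: two-sided alpha 0.05, power 0.80, a 30% difference, 63 evaluable and 70 enrolled per group. No SD is given, so 63 cannot be derived and has to be back-solved.

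- n per group = 2(1.96 + 0.84)²/d². With d = 0.5: 2 × 7.85/0.25 = 62.8, so 63.
- Conversely, d = √(2/63) × 2.80 = 0.499. If 30% means a 30-point difference between groups (an assumption), the SD is 30/0.499 = 60.1 points.
- Implied loss: 1 − 63/70 = 10%, or 7 missing values per group of 70.

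**2. Equal loss in both groups.** Power = Φ(d√(n/2) − 1.96), with d = 0.499 and n = 70 × (1 − share missing). The last column is 2 × 63/(1 − share missing), rounded up per group.

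| Missing (assumed) | Evaluable per group | Power | Total enrolment to keep 63 per group |
|---|---|---|---|
| 0% | 70 | 84.0% | 126 |
| 10% | 63 | 80.0% | 140 |
| 20% | 56 | 75.2% | 158 |
| 30% | 49 | 69.5% | 180 |
| 40% | 42 | 62.8% | 210 |

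The t-test with d = 0.5 gives 79.5%, 74.6% and 68.8% at 10%, 20% and 30%. A simulation of the planned Wilcoxon test (normal data, SD 60.1, 70 enrolled per group, 2,000 runs, loss unrelated to outcome) gives 75.8%, 70.5% and 65.6%. The mean difference stays near −30, so there is no bias.

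**3. Unequal, outcome-related loss, with missing patients left out.** Leaving is assumed to correlate 0.5 with a better creatinine course, and the group with the true benefit loses more patients. Simulated results:

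| Loss | True −30 seen as | Power | True 0 seen as | Rejection when true effect is 0 |
|---|---|---|---|---|
| 20% v 10% | −25.6 | 64% | +4.9 | 6.4% |
| 30% v 20% | −25.2 | 59% | +3.8 | 5.7% |
| 30% v 10% | −21.0 | 45% | +9.3 | 12.6% |
| 30% v 10%, unrelated to outcome | −30.0 | 72% | +0.1 | 6.0% |

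Hand check of 30% v 10%: bias = 0.5 × SD × (λ₃₀ − λ₁₀), where λ is the normal density at the cut-off divided by the share kept. λ₃₀ = 0.3477/0.7 = 0.497 and λ₁₀ = 0.1755/0.9 = 0.195, so the bias is 0.5 × 60.1 × 0.302 = 9.1 points, as simulated.

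If the patients lost are instead those with the worse course, the sign reverses by symmetry: a true −30 would appear as about −39.

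**4. Using the last in-hospital value.** Carrying it in for those without a 72-hour value (assumed correlation 0.8 with the 72-hour value, same mean; 1,000 runs) keeps all 140 patients. Simulated power is 78% to 85% across all these loss patterns, and the 30% v 10% estimate is −29.1. The equal-mean assumption favours this method. The mixed model proposed below was not simulated.

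**The case against.** Stopping therapy is not discharge. A patient who stops early but stays in hospital is still due 12-hourly panels and has a 72-hour value. Discharge before 72 hours is never mentioned, its frequency is unknown, and section 4.b points the other way on duration. All of this stands, and it limits how large the problem can be said to be. It does not close the gap, because no text secures a sample after discharge or after removal.

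Three stronger readings are tempting, and the documents do not support them.

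- A reader might infer that the plan drops early responders in a complete-case analysis. It is silent: it states neither exclusion nor imputation. Leaving such patients out is the likely default of the named test, but it is not a stated rule.
- A reader might infer that bias runs against the strategy that clears congestion faster. Treatment failures may be lost too, and the link from fast decongestion to lower creatinine is itself assumed. The net direction cannot be known.
- A reader might infer that the 12-hourly values are wasted. They have no role in the primary analysis, but they can serve the KDIGO AKI endpoint and the AKI removal rules.

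It is also fair that every loss rate above is assumed, and that at 20% v 10% the false-positive rate barely moves. A stated missing-value rule alone would close the formal gap. The model below is preferable because it uses data already collected, not because it is the only option.

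**Conclusion.** The concern holds as a gap in the primary analysis. Intention-to-treat is claimed, but the named test cannot include a patient without a 72-hour creatinine, and the plan offers only an implied 10% enrolment margin. The plan should be changed before the data are analysed.

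If loss is equal and of the same kind in both groups, the cost is power: about 80%, 75% and 69% at 10%, 20% and 30% missing, given a standardised effect of 0.5 that is back-solved and not stated in the plan. If loss is unequal and related to outcome, the comparison is also biased, by roughly 4 to 9 points in the patterns examined against a 30-point target. That range rests on an SD of 60.1, a correlation of 0.5 and assumed loss rates. Its sign in this trial is unknown.

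**What to change.** - **Primary analysis.** Fit a mixed model for repeated measures to log creatinine from all scheduled 12-hourly panels between randomisation and 72 hours. Include a discharge value only if it was drawn by 72 hours. Use baseline log creatinine as covariate and both factors by time, and report the 72-hour contrast. Back-transformed, it is a ratio, which suits a percent-change endpoint. Every patient with a post-baseline value contributes.
- **Sensitivity analysis.** Keep the Wilcoxon test, using the last in-hospital value by 72 hours for patients without a 72-hour value.
- **Data after stopping.** State that patients who stop or are removed from study treatment keep contributing the creatinine values collected while they are in hospital.
- **Text.** Reconcile section 4.a with section 4.b on treatment duration, and section 4.a (Maximum Diuretic Dose) with section 4.f on removal versus outcome follow-up. Which clinical rule applies is for the investigators to decide.

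The cost is SAP wording and modest programming, with no new samples. The downside is that the model assumes missingness is explained by observed creatinine values. If discharge depends on decongestion in ways creatinine does not show, some bias may remain.
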